## Skindex-16 Analysis of Composite Domains Scores and Individual Item Scores:

VST01
	
Output ID: t_sk_*
 
 
● Analysis Population: Intent-to-Treat Patients with measurable disease at baseline. Outputs will be repeated for Change from Baseline for Composite Domains Scores and Individual Item Scores.
 
● Column Variables: Disease Status (Locally Advanced, Metastatic)
 
● Column Totals: Totals of non-missing Disease Status
 
● Analysis Variables: Following parameters are to be summarized. 
 
○ Composite Domain (Emotion, Function and Symptom)
 
○ Individual Item (Itching, Burning Or Stinging, Hurting, Being Irritated, Persistence/Reoccurrence, Worry, Appearance, Frustration, Embarrassment, Being Annoyed, Feeling Depressed, Interaction With Others, Desire To Be With People, Show Affection, Daily Activities, Work Or Do What You Enjoy)
 
 
 
● Statistics and Calculation Methods: Use proc means or proc univariate. 
 
○ n, mean (SD), median, and min-max statistics are to be included in the table.
 
○ N in the column heading is the number of patients in a disease status in the analysis population. n in the rows is the number of patients with available data at the visit.
 
○ Change from baseline at Visit X is defined as (Visit X value – baseline value). Only patients with non-missing values at both baseline and Visit X are included in calculating change from baseline at Visit X.
 
○ All Visit after Windowing would be displayed in this table. With repeat Individual Item Score or Domain Score in a same Visit, the last non-missing Score is reported.
 
○ Individual Item Score or Domain Score collected 30 days after the last dose of study
 
 
 

---------------------	---

	
drug should be excluded from summaries of actual values and changes from baseline.
 

● Numeric Precision and Formatting of Statistics: Display 1 decimal point for Min-Max and 2 decimal points for Mean, SD and Median.

--	--

## Skindex-16 Analysis of Composite Domains Scores and Individual Item Scores:

VST01
	
Output ID: t_sk2_*
 
 
● Analysis Population: Intent-to-Treat Patients with Excludes patients with non-histologically confirmed disease. Outputs will be repeated for Change from Baseline for Composite Domains Scores and Individual Item Scores.
 
● Column Variables: Disease Status (Locally Advanced, Metastatic)
 
● Column Totals: Totals of non-missing Disease Status
 
● Analysis Variables: Following parameters are to be summarized. 
 
○ Composite Domain (Emotion, Function and Symptom)
 
○ Individual Item (Itching, Burning Or Stinging, Hurting, Being Irritated, Persistence/Reoccurrence, Worry, Appearance, Frustration, Embarrassment, Being Annoyed, Feeling Depressed, Interaction With Others, Desire To Be With People, Show Affection, Daily Activities, Work Or Do What You Enjoy)
 
 
 
● Statistics and Calculation Methods: Use proc means or proc univariate. 
 
○ n, mean (SD), median, and min-max statistics are to be included in the table.
 
○ N in the column heading is the number of patients in a disease status in the analysis population. n in the rows is the number of patients with available data at the visit.
 
○ Change from baseline at Visit X is defined as (Visit X value – baseline value). Only patients with non-missing values at both baseline and Visit X are included in calculating change from baseline at Visit X.
 
○ All Visit after Windowing would be displayed in this table. With repeat Individual Item Score or Domain Score in a same Visit, the last non-missing Score is reported.
 
○ Individual Item Score or Domain Score
 
 
 

---------------------	--

	
collected 30 days after the last dose of study drug should be excluded from summaries of actual values and changes from baseline.
 

● Numeric Precision and Formatting of Statistics: Display 1 decimal point for Min-Max and 2 decimal points for Mean, SD and Median.

--	---

## M.D. Anderson Symptom Inventory (MDASI):

MDASI contains 20 questions aimed to measure symptom severity. These questions are split across two sections.

The first section contains 14 questions. Each question asks the severity that patients feel for specific symptoms at that visit. Patients answer every question with a number ranging from 0 (“Not Present”) to 10 (“As Bad As You Can Imagine”). The 14 questions are outlined on the eCRF.

The second section contains 6 questions. Each question asks how much specific symptoms affect subjects’ lives in general. Patients answer every question with a number ranging from 0 (“Did Not Interfere”) to 10 (“Interfered entirely”). The 6 questions are outlined on the eCRF.

### Disease Related Symptoms:

The study has some specific items which are considered to be ‘Disease Related Symptoms’. These items are as follows:

Item 1: Pain

Item 2: Fatigue

Item 6: Shortness of Breath

Item 8: Lack of Appetite

Item 10: Dry Mouth

Item 14: Coughing

## MDASI Individual Item Scores:

VST01	
Output ID: t_md_*
 

● Analysis Population: Intent-to-Treat Patients with measurable disease at baseline. Outputs will be repeated for Change from Baseline for Individual Item Scores.

● Column Variables: Disease Status (Locally Advanced, Metastatic)

● Column Totals: Totals of non-missing Disease Status

● Analysis Variables: Following parameters are to be summarized.

○ Individual Items

● Statistics and Calculation Methods: Use proc means or proc univariate.

○ n, mean (SD), median, and min-max statistics are to be included in the table.

○ N in the column heading is the number of patients in a disease status in the analysis population. n in the rows is the number of patients with available data at the visit.

○ Change from baseline at Visit X is defined as (Visit X value – baseline value). Only patients with non-missing values at both baseline and Visit X are included in calculating change from baseline at Visit X.

○ All Visit after Windowing would be displayed in this table. With repeat Individual Item Score or Domain Score in a same Visit, the last non-missing Score is reported.

○ Individual Item Score collected 30 days after the last dose of study drug should be excluded from summaries of actual values and changes from baseline.

● Numeric Precision and Formatting of Statistics: Display 1 decimal point for Min-Max and 2 decimal points for Mean, SD and Median.

--------------	---

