4.2 INCLUSION CRITERIA

A patient may be included if the answer to all of the following statements is "yes."

1. Written informed consent
2. Age \geq 18 years
3. Eastern Cooperative Oncology Group Performance Status (ECOG PS) of 0, 1, or 2
4. For patients with metastatic BCC, histologic confirmation of distant BCC metastasis
5. For patients with locally advanced BCC, at least one histologically confirmed lesion 10 mm or more in diameter and written confirmation from a surgical specialist that the tumor is considered inoperable or that surgery is contraindicated. Examples of medical contraindications to surgery include but are not limited to:
 - BCC that has recurred in the same location after two or more surgical procedures and curative resection is deemed unlikely
 - Anticipated substantial morbidity and/or deformity from surgery (e.g., removal of all or part of a facial structure, such as nose, ear, eyelid, eye; or requirement for limb amputation)
6. For patients with locally advanced BCC, radiotherapy must have been previously administered for locally advanced BCC, unless radiotherapy is contraindicated or inappropriate (e.g., hypersensitivity to radiation due to genetic syndrome such as Gorlin syndrome, limitations because of location of tumor, or cumulative prior

radiotherapy dose). For patients whose locally advanced BCC has been irradiated, disease must have progressed after radiation

7. Patients with Gorlin syndrome may enroll in this study but must meet the criteria for locally advanced or metastatic disease listed above
8. Patients with measurable and/or non-measurable disease (as defined by RECIST, v1.1) are allowed.
9. Adequate organ function, as evidenced by the following laboratory results:
 - Hemoglobin >8.5 g/dL
 - Granulocyte count $\geq 1000/\mu\text{L}$
 - Platelet count $\geq 75,000/\mu\text{L}$
 - Aspartate transaminase (AST [SGOT]) and alanine transaminase (ALT [SGPT]) $\leq 3 \times$ upper limit of normal (ULN)
 - Total bilirubin $\leq 1.5 \times$ ULN or within $3 \times$ ULN for patients with documented Gilbert syndrome

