8.2.1 Types of Analyses

8.2.1.1 Efficacy Analysis

The efficacy summaries will be presented for the ITT population, which will include all patients enrolled in the study.

The efficacy variable of primary interest for this study is the overall response rate (ORR), as assessed by the Investigator according to RECIST, v1.1. The summary will be

performed on patients with measurable disease at baseline. The best overall response rate (BORR) will be reported. BORR is defined as the number of patients whose best objective response is CR or PR divided by the total number of treated patients in the group for which the BORR is estimated.

Duration of response is the key secondary efficacy variable. It is defined only for the patients whose confirmed best response is CR or PR as the time interval between the date of the earliest qualifying response and the date of PD or death for any cause. For patients who are alive without progression following the qualifying response, duration of response will be censored on the date of last evaluable tumor assessment or last follow-up for progression of disease. This will be done based on Investigator's assessments.

Time to response is defined as the interval between the date of first treatment and the date of first documentation of confirmed CR or PR (whichever occur first). This will be done based on Investigator's assessments.

Progression Free Survival (PFS) is defined as the time interval between the date of the first therapy and the date of progression or death for any causes, whichever occurs first. A patient who died without a reported progression will be considered as an event on the date of death. Patients who have neither progressed nor died will be censored on the date of last evaluable tumor assessment. This will be done based on Investigator's assessments. Patients with non-measurable disease will be assessed for disease progression and included in this summary.

Overall survival (OS) is defined as the time from the date of first treatment to the date of death, regardless of the cause of death. For patients who are alive at the time of analysis, OS time will be censored at the last date the patient was known to be alive. Patients with no post baseline information will be censored at the time of first treatment with vismodegib.

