8.2.3.2 Quality of Life Analyses and Disease Symptoms Assessment

Skindex-16

The effects of skin disease on patient's quality of life (QoL) will be accessed by the Skindex-16 questionnaire. The Skindex-16 includes three domains: symptoms, emotions and function. For ease of interpretation of scores, responses will be transformed to a linear scale of 100 varying from 0 (never bothered, i.e., best) to 100 (always bothers, i.e., worst). Distribution of scores for each domain over time will be presented by box plots and summary tables for continuous variables by means of mean, standard deviation, median, minimum, maximum, and 25th and 75th percentile. The mean scores will be presented by line graphs and corresponding 95% confidence intervals over time. Changes from baseline will be summarized by descriptive statistics and displayed together with associated 95% confidence intervals. Individual items of interest for each domain might also be summarized by frequency tables and presented by bar charts.

M.D. Anderson Symptom Inventory

The MDASI instrument will be used to determine the rate and the number of patients who have a 30% reduction in disease-related symptoms in metastatic BCC patients (e.g. pain, fatigue, shortness of breath, lack of appetite, dry mouth and coughing) following treatment with vismodegib in patients who have at least a score of 4 points at baseline.

QoL will be analyzed for the ITT population. If the safety population differs by more than 5 patients from the ITT population, then some QoL summaries might be presented for the safety population, as well.

More details will be presented in the statistical analysis plan.

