### **Intent-to-Treat Population (IT)**

The "Intent-to-Treat" population is any patient who took at least one dose of study medication according to the dose accountability CRF page. A patient was considered dosed if they had a 'number of capsules taken' record according to the exposure CRF page that wasn't zero or missing.

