## MDASI Reductions for Patients with Disease Related Symptoms:

The protocol suggests that the MDASI reduction in disease related symptoms should only be considered for patients who had four (or more) MDASI points at baseline, in order to obtain a meaningful assessment of reduction in severity from baseline. It is unclear whether this 4 points would be a patient's average baseline score, or baseline score from any domain. The following output, therefore, was created for all patients with a baseline MDASI, patients with any score of 4 or higher at baseline, and patients with an average baseline score of 4 or higher.

	Metastatic (N=XX)	Total (N=XX)
30% Reduction in Disease Related Symptoms		
n	xx	xx
Yes	xx (xx.x%)	xx (xx.x%)
No	xx (xx.x%)	xx (xx.x%)

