### Programming Note:

1. This output will be repeated for different subsets of patients.
2. MDASI was only collected for Metastatic patients, so only display the Metastatic column.
3. Percentages should be based upon the small n.
4. 30% reductions is any 30% reduction in a given analysis variable. See titles and footnotes in the lopo for these different reduction criteria.
5. N is the number of patients within the specific population.
6. Only include the questions for Disease Related Symptoms.
7. If a subject has had a reduction for the given criteria (see 30% reduction note) then they would appear in 'yes' and not in 'no'.

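### The SAP limits its only item-level MDASI table, and its first Skindex-16 table, to patients with measurable disease, although the protocol sets these summaries on ITT

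*SAP*

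**What the plan says.** **Protocol.** Section 8.2.3.2 covers both Skindex-16 and MDASI. After the MDASI paragraph it states that "QoL will be analyzed for the ITT population". Section 8.2.1.1 presents efficacy summaries for "the ITT population, which will include all patients enrolled in the study". It limits the response-rate summary to measurable disease and explicitly brings non-measurable patients into PFS. Section 8.1.2 lists both QoL and disease symptom among the efficacy variables. Inclusion criterion 8 (Section 4.2) reads "Patients with measurable and/or non-measurable disease (as defined by RECIST, v1.1) are allowed".

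**SAP.** The ITT population is "any patient who took at least one dose of study medication according to the dose accountability CRF page", the same wording as the safety population. The questionnaire outputs use these populations:

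- `t_sk_*` (Skindex-16 domains and items) and `t_md_*` (MDASI items): "Intent-to-Treat Patients with measurable disease at baseline".
- `t_sk2_*` (the same Skindex-16 content): "Intent-to-Treat Patients with Excludes patients with non-histologically confirmed disease", with no measurability condition.
- MDASI 30% reduction output: "created for all patients with a baseline MDASI, patients with any score of 4 or higher at baseline", and a further subset based on the average baseline score. A programming note adds that "This output will be repeated for different subsets of patients".

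Under Measurable/Non-Measurable Disease, the SAP takes status from a non-mandatory target-lesion box. A patient whose box is blank counts as neither measurable nor non-measurable.

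**The concern.** Measurability is a RECIST condition: it decides whether tumour shrinkage can be scored. It does not decide whether a patient can rate pain or cough. Applied to a questionnaire, the filter removes eligible, treated patients who completed the form, and it does so by a feature of the disease.

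The loss matters most for MDASI. It is collected only in metastatic patients newly enrolled after protocol version 4.0, and its impact on symptoms is a secondary objective (Protocol 2.2) in an area that Section 3.1.3 calls poorly described. The synopsis also asks for the incidence and type of symptoms at baseline in these patients. Appendix 1 classes effusions and blastic bone lesions as non-measurable, and the SAP names pain and shortness of breath as disease-related symptoms. The excluded patients could therefore have a different symptom profile, although the documents do not show that they do.

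**Working it through.** **Plan's own figure.** The only stated precision is Protocol Table 3, for adverse events. The exact limits for 120/1200 recompute to 8.36%–11.84%, matching the printed 8.4%–11.8%. No sample size or precision is given for Skindex-16 or MDASI, so there is no figure for this point to reproduce.

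**Step 1: who enters each output (SAP text).**

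| Output | Non-measurable or blank status | Not histologically confirmed |
|---|---|---|
| `t_sk_*` | excluded | included if measurable |
| `t_sk2_*` | included | excluded |
| `t_md_*` | excluded | included if measurable |
| MDASI 30% reduction | included (no condition stated) | included (no condition stated) |

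No Skindex-16 table is on full ITT. Across the two, the only patients missing altogether are those who lack both recorded measurable disease and histological confirmation. For MDASI, the reduction output shows Yes/No counts only. The other symptom table, `t_mbcc_symp_*`, sorts patients into symptomatic or not by sponsor review. Neither gives item scores at baseline or over time; only `t_md_*` does.

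**Step 2: size of the loss.** Let f be the share of the MDASI cohort recorded as measurable. The documents give neither f nor the cohort size, so f is an assumption.

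- Share dropped = 1 − f.
- Ratio of standard errors of a mean, at equal SD = 1/√f.

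| f | Dropped | 1/√f | Increase in SE |
|---|---|---|---|
| 0.95 | 5% | 1.026 | 2.6% |
| 0.90 | 10% | 1.054 | 5.4% |
| 15/18 = 0.833 | 3/18 = 16.7% | 1.095 | 9.5% |
| 0.70 | 30% | 1.195 | 19.5% |
| 0.60 | 40% | 1.291 | 29.1% |

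The 15/18 comes from the phase I study (Protocol 1.1.2.2.1), where 15 of 18 metastatic patients had radiologically measurable disease. Its exact 95% interval is 58.6% to 96.4%, roughly the range tabulated.

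**Step 3: small cohorts.** The 95% half-width for a mean, in SD units, is t(0.975, n−1)/√n. At f ≈ 0.83:

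- 15 → 12 patients: 0.554 → 0.635 (+15%)
- 20 → 17: 0.468 → 0.514 (+10%)
- 40 → 33: 0.320 → 0.355 (+11%)

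The 96 metastatic patients in the SAP mock-ups are an upper bound on the cohort: 96 → 80 gives 0.203 → 0.223 (+10%).

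**Step 4: shift in the mean.** If measurable patients have mean m and the rest mean u, the full-cohort mean is f·m + (1−f)·u. The table is then off by m − [f·m + (1−f)·u] = (1−f)(m − u). For each point by which the groups differ on the 0–10 scale, the shift is 0.05 at f = 0.95, 0.17 at f = 15/18 and 0.40 at f = 0.60. The documents say nothing about m − u, which could be zero.

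**The case against.** The strongest reply is that the protocol's main MDASI analysis is untouched. Section 8.2.3.2 asks for the rate and number of patients with a 30% reduction, and the SAP runs that on everyone with a baseline MDASI. This stands, and it rules out a reading that a reader might take from the two filtered tables, namely that all questionnaire outputs are restricted and the excluded patients' data are discarded. `t_sk2_*` rules it out for Skindex-16 as well.

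Further objections, and what is left of each:

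- **The ITT sentence says QoL, and the protocol lists QoL and disease symptoms separately.** This is fair, and its placement after the MDASI paragraph is only suggestive. But Section 8.1.2 makes disease symptom an efficacy variable and Section 8.2.1.1 presents efficacy summaries on ITT, so the point does not depend on that one sentence.
- **The tables print no intervals.** Correct: both list n, mean (SD), median and range. The figures above describe the information lost, not a column that would change. Protocol 8.2.3.2 asks for confidence intervals for Skindex-16 but not for MDASI.
- **The phase I share is a weak proxy.** Agreed. It counts radiologically measurable disease, whereas here a superficial lesion measured by caliper can be a target, which could make the loss smaller. Blank boxes could make it larger.
- **An unrestricted version may be planned elsewhere.** The SAP sends population combinations to the LoPO, which is not among the documents. One can say only that no unrestricted item-level table appears in the SAP text.

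A reader might also infer that the extension by up to 15 metastatic patients was made for MDASI. Protocol 3.2 speaks only of data on vismodegib's effect in metastatic patients, and version 4.0 data also include 8-weekly imaging and archival tissue.

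**Conclusion.** The point holds in limited form. `t_md_*` and `t_sk_*` depart from the protocol's population without a stated reason. For MDASI, the patients removed appear in no other item-level table in the SAP text. `t_md_*` also lists a locally advanced column and mentions a domain score, neither of which fits MDASI as collected and scored here. The population line may therefore have been carried over from the Skindex-16 specification, but that is inference.

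The size is uncertain: 5% to 40% of the cohort dropped and a standard error about 3% to 29% larger for measurable shares of 95% to 60%, with about 17% and 10% at the phase I share. This assumes equal spread in the two groups. Any shift in means depends on a difference that the documents do not report.

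The matter is minor. These are secondary, descriptive outputs, no hypothesis test is planned (Protocol 8.2), and no primary safety result is affected.

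**What to change.** Run `t_md_*` and one Skindex-16 table (most simply `t_sk_*`) on the SAP ITT population with neither the measurable-disease nor the histology filter, using patients with available questionnaire data at each visit. Keep the measurable-disease versions as supplementary, and leave `t_sk2_*` as it is. If the restriction was intended, state the reason in the SAP and report how many patients with a baseline questionnaire it removes, separating non-measurable disease from blank status.

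This does not restore the protocol's ITT, which is all enrolled patients against the SAP's dosed patients. The SAP should note that difference in one sentence.

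The cost is removing a filter from two existing programs, revising their titles and population lines, and rerunning them. No new data are needed.

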## MDASI Reductions for Patients with Disease Related Symptoms:

The protocol suggests that the MDASI reduction in disease related symptoms should only be considered for patients who had four (or more) MDASI points at baseline, in order to obtain a meaningful assessment of reduction in severity from baseline. It is unclear whether this 4 points would be a patient's average baseline score, or baseline score from any domain. The following output, therefore, was created for all patients with a baseline MDASI, patients with any score of 4 or higher at baseline, and patients with an average baseline score of 4 or higher.

	Metastatic (N=XX)	Total (N=XX)
30% Reduction in Disease Related Symptoms		
n	xx	xx
Yes	xx (xx.x%)	xx (xx.x%)
No	xx (xx.x%)	xx (xx.x%)

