The M.D. Anderson Symptom Inventory (MDASI) will be used to assess the impact of treatment on symptoms in metastatic BCC patients enrolled after approval of the Study Protocol, version 4.0. For these metastatic patients, incidence and type of disease symptoms will be summarized at baseline. In addition, the number of metastatic BCC patients with 30% reduction in disease-related symptoms with baseline score of 4 or more at any time during treatment will be summarized for each symptom.

Exploratory Pharmacokinetic Assessments

Individual and mean plasma vismodegib concentration versus time data will be tabulated and plotted. Plasma AAG concentration and unbound plasma concentration at selected time points will be estimated, tabulated and summarized (geometric mean, mean, standard deviation, coefficient of variation, median, minimum, and maximum). Additional PK analyses may be conducted as appropriate.

Determination of Sample Size

Approximately 1200 patients will be enrolled in this study.

Synopsis Table 1. Clopper-Pearson 95% Confidence Intervals for the observed AE incidence¹

Number of AE events/ observed AE incidence	95% Clopper Pearson Confidence Interval
12 (1%)	0.5% – 2%
24 (2%)	1.3% – 3.0%
60 (5%)	3.8% – 6.4%
120 (10%)	8.4% – 11.8%
240 (20%)	17.8% – 22.4%
360 (30%)	27.4% – 32.7%

¹ Total number of patients is 1200

Therefore, for a sample size of 1200 patients, the true AE incidence rate can be estimated to within 1.6%–1.8% assuming an observed incidence of 10%, i.e., within 95% Clopper-Pearson confidence interval of 8.4%–11.8%.

Treatment scheme:

[figure not shown]

Table 1 Schedule of Assessments

Cycle	Screening / Baseline	Treatment Phase ¹ (Allowed Visit Window +/- 3 days from Cycle 2 onwards)								End of Treatment Visit ²	Safety Follow-Up Visits ³ (1 month, 3 months, 6 months, 9 months, 12 months after the last dose of vismodegib (GDC-0499))
		1	2	3	4	5	6	7	8 onwards		
Day	-28 to -1	1	29	57	85	113	141	169	Every 28 Days		
Informed Consent ⁴	X										
Archival Tumor Tissue ⁵	X										
Medical History and Demographics ⁶	X										
Complete Physical Examination	X										
Limited Physical Examination ⁷		X	X	X	X	X	X	X	X	X	
Height ⁸ and Weight	X	X	X	X	X	X	X	X	X	X	
Vital Signs ⁹	X	X	X	X	X	X	X	X	X	X	
ECG	X	As clinically indicated								X	
ECOG Performance Status	X	X	X	X	X	X	X	X	X	X	
Hematology	X	X ¹⁰	X	X	X	X	X	X	X	X	X (if clinically indicated)
Biochemistry	X	X ¹⁰	X	X	X	X	X	X	X	X	X (if clinically indicated)

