5.6 DISEASE SYMPTOM ASSESSMENT

The M.D. Anderson Symptom Inventory (MDASI, See [Appendix 6](#)) will be used to assess the impact of treatment on symptoms in patients with metastatic BCC who enrolled after approval of the Study Protocol, version 4.0. Eligible patients will be asked to complete the questionnaire at baseline, i.e., before the start of treatment with vismodegib, at every clinic visit while receiving vismodegib, at the End of Treatment Visit, and at every Safety Follow-Up Visit.

Patients should complete the questionnaire at the beginning of each visit, before any extensive contact and consultation with the clinician/study investigator, as the consultation may bias the patient's perceptions about his or her disease symptom(s).

The MDASI core instrument is a 19-item, valid, and reliable self-report questionnaire ([34](#)) that consists of two scales that assess symptom severity and symptom interference with different aspects of a patient's life. For 13 items (pain, fatigue, nausea, disturbed sleep, distress, shortness of breath, difficulty remembering things, lack of appetite, drowsiness, dry mouth, sadness, vomiting, and numbness or tingling), patients are asked to rate how

severe the symptoms were when “at their worst” in the last 24 hours. For an additional six items, patients are asked to rate how much the symptoms have interfered with six areas of functioning (i.e., general activity, walking, work, mood, relations with other people, and enjoyment of life) in the last 24 hours. In addition to the core set of items in the MDASI, one additional symptom related to metastatic BCC will be included (coughing from the Lung Cancer module). The MDASI items are rated from 0 to 10, with 0 indicating that the symptom is either not present or does not interfere with the patient’s activities and 10 indicating that the symptom is “as bad as you can imagine” or “interfered completely” with the patient’s life.

In metastatic patients (enrolled before approval of the Study Protocol, version 4.0), disease symptoms will be assessed based on a retrospective review. A comparison of concurrent conditions and sites of metastatic disease at baseline will be used to determine disease symptoms related to metastatic disease.

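### MDASI responder output: the SAP text does not tie the 4-point baseline threshold to the symptom that falls; Skindex-16 cut-offs exceed the cited 50% missing rule in two of three domains

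*SAP*

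**What the plan says.** **MDASI.** The protocol synopsis (Disease Symptoms) says that the number of metastatic patients with a 30% fall in disease-related symptoms "with baseline score of 4 or more at any time during treatment will be summarized for each symptom". Protocol 8.2.3.2 is looser: it wants the rate and number with a 30% reduction "in patients who have at least a score of 4 points at baseline", places the reduction after vismodegib treatment, and leaves further detail to the SAP.

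The SAP (MDASI Reductions for Patients with Disease Related Symptoms) finds it unclear whether the 4 points mean an average or a score in any domain. It therefore repeats the output for everyone with baseline MDASI data, then for "patients with any score of 4 or higher at baseline, and patients with an average baseline score of 4 or higher". The table shell is a single Yes/No block without symptom rows. The programming note adds: "30% reductions is any 30% reduction in a given analysis variable. See titles and footnotes in the lopo for these different reduction criteria". It also limits the output to the six disease-related items: pain, fatigue, shortness of breath, lack of appetite, dry mouth and coughing. It states no time window. Protocol 5.6 has the questionnaire completed at baseline, at each on-treatment visit, "at the End of Treatment Visit, and at every Safety Follow-Up Visit".

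**Skindex-16.** The footnote to the SAP scoring table cites a 50% missing rule. It then sets a domain to missing only when more than 2 of 4 symptom items, more than 4 of 7 emotion items or more than 3 of 5 function items are missing.

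**The concern.** The SAP gives the purpose of the 4-point threshold: to make the reduction meaningful. A threshold on the patient does that only if the reduction is judged on a symptom that itself met it. If any item may supply the reduction, one severe, unchanged symptom admits the patient and a trivial change elsewhere supplies the response.

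The window matters too. MDASI scores run to 12 months after the last dose, so a fall recorded long after treatment could count unless the plan says otherwise.

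The other MDASI output does not fill the gap. The item tables give means and changes rather than responder counts, and their population is restricted: "Intent-to-Treat Patients with measurable disease at baseline. Outputs will be repeated for Change from Baseline for Individual Item Scores".

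For Skindex-16, the stated rule and the stated cut-offs disagree within one footnote, so a programmer cannot follow both.

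**Working it through.** **1. Skindex-16: reproduce the plan's cut-offs.** Inputs: domain sizes k = 4, 7 and 5 from the SAP scoring table. The most missing items consistent with a 50% rule is floor(k/2). The SAP's figures are matched in all three domains only by half the items rounded up, ceil(k/2).

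| Domain | k | SAP allows missing | Share | 50% rule allows |
|---|---|---|---|---|
| Symptom | 4 | 2 | 2/4 = 50.0% | 2 |
| Emotion | 7 | 4 | 4/7 = 57.1% | 3 |
| Function | 5 | 3 | 3/5 = 60.0% | 2 |

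One response step on one item moves the domain score by (100/6)/(items answered). At the limit:
- Function: 16.67/2 = 8.3 points under the SAP, 16.67/3 = 5.6 under the rule.
- Emotion: 16.67/3 = 5.6 under the SAP, 16.67/4 = 4.2 under the rule.
- Symptom: 16.67/2 = 8.3 under both.

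**2. MDASI: smallest whole-point fall that reaches 30% on the 0-10 scale.**
- Baseline 1, 2, 3: 1 point (100%, 50%, 33.3%).
- Baseline 4, 5, 6: 2 points (50%, 40%, 33.3%). A 1-point fall from 4 is 25%.
- Baseline 7, 8, 9, 10: 3 points (42.9%, 37.5%, 33.3%, 30%).

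A 1-point fall therefore reaches 30% only from baselines below the threshold.

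**3. One patient under different readings.** Pain 5 to 5, cough 1 to 0, the other four items 0 throughout. The patient is in the any-score set because of pain.
- Any of the six items may supply the reduction: Yes.
- Output repeated by symptom, with no baseline limit on that symptom: Yes for cough, No for pain.
- Reduction in the six-item average (an assumption, since the SAP does not name the items averaged): (5+1)/6 = 1.00 to 5/6 = 0.83, a 16.7% fall, so No.
- Threshold and reduction on the same symptom: not in the cough denominator; in the pain denominator as No.

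The classification thus turns on criteria that the supplied SAP text leaves to the LoPO. Repeating the output by symptom would not be enough without the baseline limit.

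**4. The average set.** Pain 10, fatigue 10, other four items 0: 20/6 = 3.33, below 4 on the same six-item assumption. The patient is left out of this set although two symptoms score 4 or more.

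**5. Window.** The synopsis refers to treatment; 8.2.3.2 can be read as including later scores. The item tables carry a limit ("Individual Item Score collected 30 days after the last dose of study drug should be excluded"), but it is not repeated for the responder output. It would not cleanly separate the phases either: the 1-month visit, at 30.4 days plus or minus 5, falls between about day 25 and day 35.

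**The case against.** The strongest reply is that the MDASI defect depends on a document that is not supplied. The programming note speaks of several reduction criteria and sends them to the LoPO, which may contain symptom-level repeats with a baseline limit. This stands. A reader might infer that the trial will count trivial falls as responses; the documents do not show that, only that the SAP text does not prevent it.

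The synopsis is also less decisive than it looks. It fixes the level of reporting (by symptom) more clearly than the level of eligibility, because the 4-point condition can attach to the patient or to the symptom. Section 8.2.3.2 attaches it to the patient and delegates detail to the SAP, which disclosed the ambiguity and planned three versions. So the SAP cannot be said to contradict the protocol on eligibility. The absence of symptom rows in its shell remains.

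A reader might also infer that all follow-up scores must be excluded. Section 8.2.3.2 does not support that; the two protocol passages need reconciling.

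Nor does the average-of-4 example show a patient lost from the analysis. The same patient is in the all-patients and any-score versions.

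On Skindex-16, the cut-offs are a consistent rounding up of half the items, and the compliant symptom domain already tolerates the 8.3-point sensitivity seen in function. The practical gain is modest, but the mismatch with the cited rule remains.

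**Conclusion.** Both discrepancies are real and minor. For MDASI, the supplied SAP text offers only patient-level thresholds and a single Yes/No block where the synopsis asks for a summary by symptom. It does not tie the threshold to the symptom that falls, and it gives no window. How many patients would be classified differently cannot be derived from the documents. For Skindex-16, two of three domains are scored with more than half their items missing (57.1% and 60.0%). The effect depends on item non-response, which is not given, and is probably small.

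Both outputs are secondary and descriptive, and no hypothesis test is planned, so no error rate is affected.

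Timing limits what can be claimed for a preferred version. The SAP says in the past tense that the MDASI output was created. The specification is dated 14 September 2015 and contains filled tables, among them a deaths table run on 10 September 2015. A reader might infer that a definition was picked after seeing results. The MDASI shell is blank and nothing supports that inference, but a main version named at this stage should be called post hoc.

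**What to change.** **MDASI.**
- Add one row for each of the six disease-related symptoms. Denominator: metastatic patients with a baseline score of 4 or more on that symptom. Numerator: those with at least a 30% fall on the same symptom.
- Keep the three existing versions as supportive, state which items form the average, and write the LoPO reduction criteria into the SAP.
- Reconcile the window between the synopsis and 8.2.3.2 and state it. If follow-up scores are kept, show on-treatment results separately.
- Label any choice of main version as post hoc.

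**Skindex-16.** Set a domain to missing if more than 2 of 4 symptom, 3 of 7 emotion or 2 of 5 function items are missing.

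**Cost.** SAP wording and programming only; no new data. The MDASI rows will have small denominators of unknown size: the SAP's deaths table shows 96 metastatic patients in the safety population, and MDASI covers only those newly enrolled after protocol version 4.0, a count that is not given. With an assumed 10 or 20 patients per symptom, an observed 50% would have a Clopper-Pearson 95% interval of 18.7% to 81.3% or 27.2% to 72.8%. A few more Skindex-16 domain scores would become missing.
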